# Inclusion Criteria

- 1. Females and males 18 years or older.
- 2. History consistent with seasonal allergic rhinitis consistent with grass allergy (symptoms during summer months, June through August, for at least two consecutive seasons).
- 3. Not currently taking any medications for allergic rhinitis.
- 4. Provide written informed consent.
- 5. Willing and able to comply with all aspects of the protocol.

#### Exclusion Criteria

- 1. The subject has any uncontrolled or serious disease, or any medical or surgical or condition that in the opinion of the investigator(s) could affect the subject's safety and/or interfere with the study assessments.
- 2. History of anaphylaxis to environmental allergens.or an unknown trigger.
- 3. History of broccoli allergy.
- 4. Recent upper respiratory infection (less than 4 weeks prior to study) or other active Infection.

- 5. Active smoker.
- 6. Currently receiving allergy immunotherapy.
- 7. History of rhinitis exacerbation within the past 2 weeks.
- 8. Use of non-selective Beta-Blocker.
- 9. Inability to give written informed consent.
- 10. History or evidence of non-stable cognitive capacity within less than 1 year (i.e. Alzheimer's disease, dementia, bipolar disorder) that in the opinion of the investigator(s) could affect the subject's safety and/or interfere with the study assessments.
- 11. Pregnancy.
- 12. Perennial rhinitis.
- 13. Uncontrolled asthma.
- 14. FEV1 (forced expiratory volume in 1 s) <70% predicted at screening.

# Recruitment:

In order for 152 subjects to complete the study, 475 subjects will be recruited for enrollment under the assumption 50% (237) of subjects will have seasonal allergic rhinitis to grass confirmed on skin testing, 80% (190) of subjects will have a positive nasal challenge and 80% (152) of subjects will complete the study.

Subject recruitment will occur at three facilities: VA Greater Los Angeles Health Care System (VA GLA), VA Long Beach Health Care System (VA LB) and the University of California Los Angeles (UCLA) Medical Center. Within each facility, recruitment will occur at primary and specialty (allergy) clinics.

#### Recruitment at VA Greater Los Angeles and VA Long Beach Health Care Centers: Primary Care Clinic Recruitment:

Investigators will work together with providers assigned to Patient Aligned Care Teams (PACT). On average, PACTs follow 44,000 patients at VA Long Beach and 63,000 at VA Greater Los Angeles. Assuming involvement with primary care providers following 10,000 subjects at VA GLA and 10,000 subjects at VA LB, At each facility, 2,000 (20%) will should have a diagnoses of allergic rhinitis. 600 (30%) will experience allergic rhinitis symptoms during the summer months and 300 (50%) of these subjects will have symptoms limited to summer months. We estimate at total of 600 potential recruitment subjects from primary care clinics at both VA GLA and VA LB.

# Allergy Clinic Recruitment:

Within the past year, 40% (320) of new consultations at VA Greater Los Angeles Healthcare System and 68% (208) of new consultations at VA Long Beach Healthcare System were requested to evaluate allergic rhinitis. Based on these figures, we would anticipate a total of 30% having allergic rhinitis associated with summer months and then 50% of these patients having allergic rhinitis limited to summer months or 79 (48 + 31) potential subjects at VA GLA and VA LB combined.

# Recruitment at the University of California Los Angeles Medical Center:

In Southern California, patients are seen at 16 satellite primary care clinics affiliated with UCLA Medical Center. Adult Allergists practice at four of these locations (Porter Ranch CA, Santa Monica CA, Thousand Oaks CA, Torrance CA.) Investigators will work with providers at UCLA affiliated clinics in identifying potential subjects. (see Contingency Plan)

# Use of Flyers at Institutions:

In addition to the above recruitment strategy, flyers will be placed in primary care, ear nose and throat, and dermatology clinics at VAGLAHS and VALBHCS with contact information for enrollment. Potential subjects who call will be preliminary screened via phone call screening script to determine possible eligibility. Those who pass the preliminary screening process will have an appointment scheduled.

# **Recruitment from VA GLA Pharmacy Database:**

In addition, we will work with pharmacy to retrieve patients prescribed nasal corticosteroids limited to summer months. These patients have a higher likelihood of suffering from grass pollen allergic rhinitis.

# **Contingency Plan:**

Participation recruitment will be followed closely. If needed, we will submit a request for expansion to involve non veterans. The VA GLA is close to UCLA. Students/staff/potential subjects attending UCLA may qualify for inclusion into the study.

# **Medical History:**

A medical history will be obtained to confirm whether patient has clinical symptoms consistent with summer seasonal rhinitis (during grass season) allergic rhinitis.

# **Procedures at Each Visit:**

Consenting (<20 days to Visit 1)

-Affirm eligibility, check medication use.

-Review study with patient and if subject agrees to enroll, obtain subjects written informed consent.

-Instructions for avoidance of sulforaphane containing food products in diet.

- Review concomitant medication use.
- -Instructions for avoidance of the following medications: oral antihistamines, nasal corticosteroids, nasal mast cell stabilizers, nasal antihistamines, leukotriene antagonists.
- -Proceed onto visit 1, or schedule subject for visit 1  $\leq$  20 days from providing written consent.

Visit 1 (Day 1)

-Spirometry performed (Note: subjects' have up to 3 attempts to FEV1 of  $\geq$ 70% to continue on with this study).

- -Collect blood pressure, heart rate, height and weight.
- Check concomitant medication use since last visit.
- -General physical examination.

-Nasal examination.

-Epicutaneous Allergen Skin Testing. Patients who qualify based on skin test results will proceed with up-dosing nasal challenge to the positive skin test grass allergen. Subjects that have completed epicutaneous allergen skin or blood test at the VA Allergy Service within  $\leq 1$  year with positive results to grass pollens will to proceed onto the up-dosing nasal challenge using the results on file.

-Updosing nasal challenge. Patients with positive nasal challenge will continue as follows: -Obtain blood work to determine sulforaphane baseline level and genotype for GSTM1 polymorphisms.

- Schedule subject for visit 2.

### Visit 2 (Day 14)

-Check concomitant medication use since last visit.

-Collect blood pressure, heart rate and weight.

- -Spirometry performed
- -General physical examination.
- -Nasal examination.
- -nasal lavage
- -Obtain blood work for sulforaphane level check.
- -Grass Nasal Challenge.
- -Randomize patients into one of four groups.
- -Medication Dispensing (to begin evening of Day 15).

# Visit 3 (Day 35)

-Check concomitant medication use since last visit.

- Collect medication dispensed at last visit (research team complete medication compliance).
- -Collect blood pressure, heart rate and weight.
- -Spirometry performed
- -General physical examination.
- -Nasal examination.
- -Nasal lavage
- -Obtain blood work for sulforaphane level check.

-Grass nasal Challenge.

### Study Schedule:

The typical schedule is shown as an example for consenting.

#### Consenting (<20 days prior to visit 1) Activitity (in sequence):

Affirm eligibility, check medication use.

Review study with patient and if subject agrees to enroll, obtain subjects written informed consent.

Instructions for avoidance of sulforaphane containing food products in diet prior to visit 1 and throughout the study.

Instructions for avoidance of the following medications: oral antihistamines, nasal corticosteroids, nasal mast cell stabilizers, nasal antihistamines, leukotriene antagonists prior to visit 1 and throughout the study.

Proceed onto visit 1, or schedule subject for visit 1 within  $\leq$  20 days from providing written consent.

The typical schedule is shown as an example for the enrollment visit (Visit 1).

#### Visit 1 (Day 1) Activity (in sequence):

Subject arrives at the Allergy/Immunology Clinic.

Spirometry will be performed before skin test. (Note: subjects' have up to 3 attempts to FEV1 of  $\geq$ 70% to continue on with this study.)

Vital signs will be collected (heart rate, blood pressure, weight, height) and general physical examination along with nasal examination.

Subjects undergo epicutaneous skin testing. (Subjects who qualify based on skin test will continue with nasal challenge). For subjects who have an epicutaneous allergen skin or blood test on file completed by the VA Allergy Clinic within  $\leq$  1 year that confirms a positive to grass pollens the results will be used to proceed onto the up-dosing nasal challenge.

Up-dosing nasal allergen challenge will be performed

Subjects testing positive to nasal challenge will proceed with blood work to check sulforaphane Baseline levels and genotype for GSTM1 polymorphisms

The typical schedule is shown as an example for a follow up evaluation day for visit 2.

#### Visit 2 Activity (in sequence):

Subject arrives at the Allergy/Immunology Clinic.

Vital signs (heart rate, blood pressure and weight), *nasal examination*, concomitant medication and diet checked since last visit.

Spirometry will be performed. (Note: subjects' have up to 3 attempts to FEV1 of  $\geq$ 70% to continue on with this study.)

general physical examination along with nasal examination.

Nasal lavage performed.

Blood work obtained for sulforaphane level

Nasal allergen Challenge followed by monitoring explained below

Randomization occurs. Instructions for avoidance of sulforaphane containing food products in diet and for avoidance of medications reiterated.

The typical schedule is shown as an example for a follow up evaluation day for visit 3.

Visit 3 Activity (in sequence):

Subject arrives at the Allergy/Immunology Clinic.

Study medication disepensed at visit 2 are returned by the subject and a compliance check is performed the study team.

Vital signs (heart rate, blood pressure and weight), *nasal examination*, concomitant medication and diet checked since last visit.

Spirometry will be performed. (Note: subjects' have up to 3 attempts to FEV1 of  $\geq$ 70% to continue on with this study.)

general physical examination along with nasal examination.

Nasal lavage performed.

Blood work obtained for sulforaphane level.

Nasal Allergen Challenge followed by monitoring explained below

Study completed.

### Study Outcome Measures:

1. The Total Nasal Symptoms Score (TNSS), performed to determine adequate dosing for nasal challenge (visit 1) and during the nasal challenges (visit 2, 3). During the challenge the TNSS will be taken 30 minutes after nasal lavage, and then repeated at 5, 15, and 30 minutes then hourly to 4 hours post-challenge.

2. The peak nasal inspiratory flow (PNIF) performed at the up-dosing nasal challenge visit (visit 1) and during nasal challenges (visit 2 and 3). During the challenge, PNIF will be taken 30 minutes after the nasal lavage, then repeated at 5, 15 and 30 minutes after the challenge, then hourly to 4 hours post-challenge.

3. Biomarker measurements taken from nasal fluid collected by nasal sponge at visit 2 and visit 3 will include:

a) IL-4: 0 mintue, 5 minutes, 15 minutes, 30 minutes, then hourly to 4 hours post challenge
b) IL-5: 0 minute, 5 minutes, 15 minutes, 30 minutes, then hourly to 4 hours post challenge
c) IL-13: 0 minute, 5 minutes, 15 minutes, 30 minutes, then hourly to 4 hours post challenge
d) Eosinophil Cationic Protein (ECP): 0 minute, 5 minutes, 15 minutes, 30 minutes, then hourly to 4 hours post challenge

e) Tryptase: 0 minute, 5 minutes, 15 minutes, 30 minutes, then hourly to 4 hours post challenge

# **Study Regimen:**

#### Study Medications and Placebo

Nasal Corticosteroids: Fluticasone propionate nasal spray prescribed as 2 sprays in each nostril daily will be the nasal corticosteroid of choice for the current study. Placebo will be normal saline based. Both fluticasone and placebo will be ordered through the VAGLAHS Research Pharmacy. For optimal control of nasal symptoms a treatment period of 1 week is required. Fluticasone will be given for 3 weeks in order to maximize effect.

Active Avmacol Enteric Coated Tablets:Water, HPMC, Sodium Alginate, Purified Stearic Acid, Ethylcellulose, Medium Chain Triglycerides, Oleic Acid, Triactin, Mineral Oil, Sodium Lauryl Sulfate, Titanium Dioxide

Avmacol, a blend of broccoli seed and sprout extracts contains the 2 essential ingredients needed for sulforaphane production: glucoraphanin and the myrosinase enzyme. Avmacol contains  $\sim$  30 - 35 umoles sulforaphane per 2/tablet recommended serving.

# Placebo Avmacol Coated Tablets:Water, HPMC, Triactin, Mineral Oil, Sodium Lauryl Sulfate, Titanium Dioxide

# **Concomitant Medications**

Concomitant medication is defined as any medication, which is taken during the study. All prescription, herbal supplements, and over-the-counter drugs which are being taken by subjects upon entry to the study or which are taken during the study are regarded as concomitant treatments and will be documented. Basic medication use information will be confirmed at the time of screening, in order to determine if subject meets exclusion criteria regarding medications.

# Rescue Medications

Subjects in the study are atopic. During the course of the study, subjects may develop nasal symptoms. They will be allowed to treat their symptoms with saline nasal spray. If their symptoms persist and they require additional medications, they will be discontinued from the study.

# Prohibited Medications

The days below indicate last dose received prior to visit 1 and throughout the subjects' total participation time:

- 1. Topical Nasal Steroid use in the past 14 days,
- 2. Systemic steroid use in the past 14 days,
- 3. Oral antihistamine use in the past 5 days,
- 4. Intranasal antihistamine or cromolyn use in week prior to nasal challenge.
- 6. currently receiving allergy immunotherapy, or use anytime during the protocol.
- 7. short acting beta agonists in the past 6 hours.
- 8. nasal cromolyn in the past 7 days,
- 9. oral decongestants in the past 3 days,
- 10. antihistamine-decongestant tablets/liquids in the past 3 days,

# Nasal Sprays:

Both the active fluticasone proprionate (50mcg) and the placebo will be obtained from the VA Research pharmacy.

# Criteria for Premature Termination of the Study

# Participant Withdrawal Criteria

In the best interest of the subject, participants may be prematurely terminated from the study for the following reasons:

1. The participant elects to withdraw consent from all future study activities, including follow-up.

- 2. The participant is "lost to follow-up"
- 3. The participant takes any of the prohibited medications during the study.
- 4. The participant develops an adverse event that, in the opinion of the Protocol Chair (Principal Investigator) or the Safety Monitoring Board of the study, increases his/her

risks if study participation continues.

5. The participant dies

### Study Stopping Rules

The Data Safety Monitoring Board (DSMB) will be provided summaries of all adverse events on a regular basis. The DSMB will have the authority to terminate the trial at any time based on reported adverse events.

Study enrollment and ongoing study treatments will be suspended pending expedited review of all pertinent data by the VAGLAHS Institutional Review Board (IRB), the Data Safety Monitoring Board (DSMB) if a significant adverse event *as deemed by DSMB* occurs that is possibly related to the study procedures. The study may be terminated by the DSMB upon review of data with observations or findings that such action is necessary. (National Cancer Institute's Common Terminology Criteria for Adverse EventsVersion 4 (published May 28, 2009)).

Grade 1=Mild adverse event Grade 2=Moderate adverse event. Grade 3=Severe and undesirable adverse event Grade 4=Life-threatening or disabling adverse event Grade 5=Death

# **Screening Visit**

At the screening visit, potential subjects are given a copy of the IRB-approved informed consent form for review and are invited to ask any questions or express concerns after reading the consent. The research study is clearly explained to the subject, including the rationale, risks, and benefits. The subject is asked to explain what he/she understands to be required in the study. The subject is informed that all participation is voluntary and that he/she is free to discuss the study with family or friends when considering enrollment. Subjects are told that only if the study protocol is fully understood should they sign the consent form. After the subject provides written consent, potential subjects' eligibility will be confirmed based on the determined inclusion/exclusion criteria. Once the subject has signed the informed consent form, a study investigator will also sign it, and the subject will receive a copy.

#### Procedures performed

Skin Testing: Epicutaneous skin testing is considered highly reliable, safe and widely used in diagnosing allergic rhinitis (37). After application of the specific allergen to the sterile tip of the applicator, the subject's skin will be gently lifted and the tip containing allergen will be applied. Along with application of the allergens mentioned, histamine and a saline control will be applied to subject's skin. Results will be interpreted 20 minutes following and will be considered positive if the wheal and erythema are at least 3mm larger than the saline control. For subjects who have an epicutaneous allergen skin or blood test on file completed by the VA Allergy Clinic within  $\leq 1$  year that confirms a positive to grass pollens the results will be used to proceed onto the up-dosing nasal challenge.

Nasal Challenge: Nasal Challenge is considered a safe and useful diagnostic tool in diagnosing causes of both allergic and nonallergic rhinitis *(38)*. The nasal challenge chosen was based on repeated reliability using the TNSS and PNIF scores along with the biomarkers chosen for this study. (36)

Subjects will undergo an up-dosing nasal challenge performed at visit 1 in order to determine the threshold dose to be given at the subsequent nasal challenges (visit 2 and visit 3). During the up-dosing nasal challenge, the TNSS will be recorded immediately before each subsequent dose. Grass allergen extract (*c. cynodon, p. pretense or s. sorghum*,) will be used in the

challenge. For c. cvnodon (Bermuda grass), dosing will start at 30 BU/ml and will continue with the following concentrations until a TNSS score reaches 7 or greater or PNIF is reduced by >50% from baseline reading: 300, 1000, 3000 and 10,000 BU/ml. For p. pretense(Timothy grass), dosing will start at 300 and will continue with the following concentrations until a TNSS score reaches 7 or greater or baseline PNIF is reduced by > 50% from baseline reading: 1,000,3,000,10,000 and 100,000 BU/ml. For s. sorghum (Johnson grass) dosing will start at 1:200,000 and will continue with the following concentrations until a TNSS score reaches 7 or greater or baseline PNIF is reduced by > 50% from baseline reading: 1:20,000, 1:2000, 1:200, and 1:20 w/v. Subjects will receive three sprays equivalent to 100 µl for each concentration into each nostril using an atomizer device, part of the standardized equipment at VAGLAHS for patients requiring nasal sprays during procedures applied every 10 minutes until maximal concentration or a TNSS score of 7 or PNIF reduction by  $\geq$  50% from baseline reading is achieved. Prior to subsequent challenges at visit 2 and 3, nasal lavage (SinusRinse) will be performed. A baseline PNIF and TNSS will be recorded 30 minutes following nasal layage for visits 2 and 3. Nasal challenge with 100 µl of the final dose achieved at visit 1 will then be applied into each nostril. The PNIF and TNSS will be recorded following challenge at 5, 15, 30 minutes following challenge and then at 1 hour, continuing to record each hour for 4 hours. During these intervals, nasal sponges (Plastocell & Co.) will be applied into each nostril onto the nasal mucosa, beyond the nasal vestibule, and alongside the inferior turbinate with the use of a crock forceps (Phoenix surgical instruments, Harlow, UK) and a Thuddicum's nasal speculum (Phoenix surgical instruments, Harlow, UK). After two minutes of placement, the sponges will be removed and then added to 2 ml centrifuge tubes with indwelling .22µm cellulose acetate filters (Costar Spin-X, Corning, NY, USA) and placed immediately into ice before centrifuging within the hour. The liberated fluid will then be freezed at -80° until analysis occurs.

General physical examination: A physical examination to determine general health to include measurement of vitals and a cardiopulmonary examination will be performed in the VA GLA Allergy/Immunology Clinic by the attending physician. A *nasal examination* will be performed at every visit before any nasal challenge or lavage is performed. On Day 1, a urine pregnancy test will be performed for women of child-bearing potential.

The Immediate Total Nasal Symptom Score (TNSS): The TNSS has been used in prior interventional studies to evaluate different treatment modes for allergic rhinitis (*39, 40*, and 41). The score will consist of subjects rating 4 symptoms (nasal congestion/postnasal drainage, nasal pruritus, rhinorrhea, or sneezing) on a scale of 0 to 3, where 0=no symptoms present, 1=mild symptoms that do not interfere with activity, 2=moderate symptoms that are slightly bothersome symptoms with slight interference with activity and/or nighttime sleep, or 3=severe symptoms with interference with activity and nighttime sleep.

The Peak Nasal Inspiratory Flow (PNIF): the PNIF (Alliance Tech Medical) has been used in prior interventional studies involving allergic rhinitis (42, 43, and 44). Patients exhales fully and quickly after checking that an air tight seal covers the nose and seals the mouth.

Nasal Examination: Nasal examination will be performed at each visit prior to nasal challenge. Each nasal examination will include use of an otoscope with specula inserted into the nasal passage. Nasal passages and nasal turbinates will be inspected for color, swelling, exudate or bleeding.

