At visit 2 (2 weeks following visit 1) and visit 3 (5 weeks following visit 1), subjects will undergo a single nasal allergen challenge with the effective dose determined during the up-dosing challenge at visit 1. Total nasal symptom score and peak nasal inspiratory flow will be recorded throughout all nasal challenge procedures.

Biomarkers collected through sponges placed in both nasal passages during the challenge will include IL4, IL5, IL13, eosinophil cationic protein and tryptase. At the end of visit 2, patients will be randomized and will be instructed to begin the following evening, to return in 3 weeks for another nasal challenge.

Throughout the study, serum sulforaphane levels for each subject will be checked at visits 1, 2 and 3 to monitor adherence.

All study procedures will be conducted at the VAGLAHS. Subjects will be assigned an appointment day and appointment time for each scheduled visit. All appointments will be at approximately the same time of the day for all subjects to avoid diurnal variation.

Figure 1. Overview of Study Procedures

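### The only pregnancy test the plan specifies is on Day 1, about two weeks before randomisation and first dose; repeat it at visits 2 and 3 and say what a positive result means.

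*Combined protocol and SAP*

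**What the plan says.** Under Exclusion Criteria, item 11 is pregnancy and item 8 is "Use of non-selective Beta-Blocker". Neither is limited to screening, whereas item 14 (FEV1) is.

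The pregnancy test appears in Procedures performed, in the paragraph on the general physical examination: "On Day 1, a urine pregnancy test will be performed for women of child-bearing potential". The same paragraph puts the nasal examination at every visit. No other section of the supplied text specifies a pregnancy test.

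The Overview of Study Design places allocation after the second challenge: "At the end of visit 2, patients will be randomized". The Visit 2 (Day 14) list has the entry "Medication Dispensing (to begin evening of Day 15". Visit 3, with the final challenge, is on Day 35.

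On medication, the activity lists for visits 2 and 3 include "concomitant medication and diet checked since last visit", and Concomitant Medications says of drugs that they are recorded if taken in the trial: "which are taken during the study are regarded as concomitant treatments and will be documented". The Prohibited Medications list opens with "The days below indicate last dose received prior to visit 1 and throughout the subjects' total participation time". Its printed items name no beta-blocker, and its numbering goes from 4 to 6.

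**The concern.** A pregnancy test done to enforce an exclusion should be current when the subject is allocated and first exposed. Here it is tied to the up-dosing visit. A pregnancy too early to detect on Day 1, or one that begins in the following two weeks, would pass through the visit 2 challenge, randomisation and the start of treatment without meeting any specified test. All study treatment and two of the three allergen challenges come after the only test.

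The plan also does not say what follows if a pregnancy is found after entry. The same question arises, more narrowly, for a non-selective beta-blocker started after randomisation: the drug is an exclusion, the plan prepares for hypersensitivity reactions including anaphylaxis (Precautions), and one allergen challenge remains.

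What is at stake is subject safety. The estimate of the treatment effect is not affected.

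**Working it through.** **Inputs.** Test: Day 1 (Procedures performed). Visit 2 challenge and randomisation: Day 14; first dose: evening of Day 15 (Visit 2 list). Visit 3 challenge: Day 35 (Visit 3 list). Window: ±10 days (Visit Target Windows). Randomised 190, completing 152 (Recruitment; Sample size consideration). The plan gives no figure of its own on this point to reproduce.

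**Age of the test at each exposure.**
- Visit 2 challenge and randomisation: 14 − 1 = 13 days. The window is stated for the treatment phase; if it also covers visit 2 (Day 4 to 24), the range is 4 − 1 = 3 to 24 − 1 = 23 days.
- First dose: 15 − 1 = 14 days.
- Visit 3 challenge: 35 − 1 = 34 days; with visit 3 on Day 25 to 45, 25 − 1 = 24 to 45 − 1 = 44 days.

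**Treatment after the only test.** Evenings from Day 15 to Day 34: 34 − 15 + 1 = 20. With visit 2 on Day 14 and visit 3 moved within its window: 24 − 15 + 1 = 10 to 44 − 15 + 1 = 30.

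**Women affected.** The share of women of child-bearing potential is not in the documents, so it is assumed. Women dosed with no further specified test = 190 × share:
- 5%: 190 × 0.05 = 9.5, about 10
- 20%: 190 × 0.20 = 38
- 30%: 190 × 0.30 = 57

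**Expected pregnancies.** This is an illustration with every rate assumed. Take 2% to 10% of these women conceiving per year:
- Low end, 34 days: 10 × 0.02 × 34/365 = 0.02
- High end, 34 days: 57 × 0.10 × 34/365 = 0.5
- High end, with 21 days added for conceptions too early to detect on Day 1: 57 × 0.10 × 55/365 = 0.9

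Even the high end is below one.

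**Strips needed for the fix.** One per woman at visit 2 and one at visit 3 = (190 + 152) × share = 342 × share: 17 at 5%, 68 at 20%, 103 at 30%.

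**Beta-blocker, by reading.** Exclusion 8 has no screening limit, so it can be read as holding up to randomisation at the end of visit 2. What remains is one challenge, at visit 3, 35 − 14 = 21 days later (11 to 31 if visit 3 moves and visit 2 stays on Day 14). Medication is checked before that challenge, but the printed text states no action if a beta-blocker is found.

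**The case against.** *The visit schedules are not exhaustive.* True. They are introduced as illustrations, for instance "The typical schedule is shown as an example for a follow up evaluation day for visit 2", and the visit 1 lists leave out the pregnancy test that is plainly intended there. Its absence from the visit 2 and 3 lists therefore proves nothing. The point rests on the sentence that fixes the test to Day 1, beside another in the same paragraph that makes the nasal examination a procedure for every visit.

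*Very few pregnancies would occur.* This also stands. The illustration gives fewer than one, and the documents state no pregnancy-specific harm from three weeks of nasal steroid or broccoli extract. It limits the weight of the point. It does not remove it, because the plan itself excludes pregnancy and the remedy is a urine strip.

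*The consent pages may carry pregnancy instructions.* They were removed, so this cannot be judged. Contraception or reporting advice there would supplement a current test before dosing but would not replace it.

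*A stop rule may already exist for beta-blockers.* This is the strongest objection to the secondary point. Item 5 of the prohibited list is missing from the supplied text, and whether a line was lost or the numbering slipped is unknown. If item 5 names beta-blockers, that list and withdrawal criterion 3 (taking a prohibited medication) largely deal with the matter. The visit 3 challenge also repeats a dose already given at visit 2, and it follows spirometry and a physical examination in a clinic equipped for anaphylaxis.

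*Stronger readings a reader might infer.* One is that the plan lets pregnant women continue, because its withdrawal list is worded permissively. The documents do not support that: the same list includes withdrawn consent and death, so the permissive verb shows little, and nothing directs continued exposure. Another is that the 342 planned challenges after Day 1 measure the exposure. That figure counts every subject, men included.

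**Conclusion.** The point holds for test timing. The only specified pregnancy test is 13 days old at the visit 2 challenge and randomisation, 14 at first dose and 34 (24 to 44) at the last challenge, although pregnancy is an exclusion. The day counts come straight from the plan. The 10 to 57 women are an assumption-based range, and the expected number of pregnancies is below one on the rates assumed. This is a cheap safety improvement and not a flaw in the design.

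The beta-blocker point is secondary. It is conditional on what item 5 of the prohibited list contains, and it reaches the visit 3 challenge only. A reader might go further and want the spray and tablets stopped for a new beta-blocker. Nothing in the documents gives a reason for that.

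**What to change.** 1. In Procedures performed and in the visit 2 and 3 lists, repeat the urine pregnancy test for women of child-bearing potential: at visit 2 before the challenge and randomisation, and at visit 3 before the challenge. The visit 2 test matters most, because it precedes all study treatment.
2. Add one sentence: a positive result means that no challenge is performed and no study treatment is started or continued. The FEV1 rule in the Overview of Study Design is a ready model for the wording.
3. Confirm what item 5 of Prohibited Medications contains. If it does not cover non-selective beta-blockers, add them, and state that the visit 3 challenge is not performed if the existing medication check finds one. Do not require study treatment to stop for that reason.

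**Cost.** A short amendment and up to two urine strips per woman of child-bearing potential, at visits that already take blood and examine the subject. A positive test at visit 2 stops the subject before allocation. A cancelled visit 3 challenge leaves a rare randomised subject without the visit 3 TNSS, the primary outcome. The planned multiple imputation would cover that missing value.
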